3.3. Treatment Assignment

Eligible subjects will be randomized to study vaccine or placebo in a 2:1 ratio. Subjects will be stratified by HAI titer.

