8.2. Subject Disposition and Baseline Characteristics

8.2.1. Sample size

The sample size of 15 subjects per cohorts 1 and 2, and 90 subjects per cohort 3 were chosen based on reports of studies of other vaccines in early-stage development. This study is not powered for any formal comparisons. See Section 1.4 for probability of detecting an AE. Subject Characteristics Data Set

Demographics will include by-treatment summaries of age, height, weight, body mass index (BMI), race, ethnicity, and gender.

Other baseline characteristics may be summarized.

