1.1. Statistical and Analytical Plans

1.1.1. Definitions and General Considerations for Data Analysis

- 1. This Statistical Analysis Plan (SAP) is based on Clinical Trial Protocol FluGen-H3N2-V002-V005 dated 10-May-2021 (v2.0).
- 2. All programming and calculations will be performed using SAS statistical software, version 9.4 or later.
- 3. Study Day 1 is the day of randomization and 1st IP administration; QIV administration is planned 28 Days after IP administration
- 4. Baseline (IP Baseline) is the last observation prior to IP administration, at the datapoint, not the record level. For example, for laboratory values, individual repeat tests values will be used for baseline when the entire panel may not have been repeated.
- 5. Summaries will be presented by treatment and age group and for all ages combined. Cohorts 2 and 3 will not be presented separately.
- 6. This study is not powered to detect differences in safety or immunogenicity between active and placebo groups. The sample size of 120 (80 active subjects and 40 placebo subjects) was chosen empirically based on studies of other vaccines in early-stage development.
- 7. There is no plan for test of hypotheses; p-values generated for immunogenicity are descriptive only and not adjusted for multiplicity.
- 8. For transparency and traceability, raw data, not results from calculations or corrections are to be transferred from external vendors. Differences between data transferred versus data as analyzed, will be documented in the CSR.
- 9. The clinical database will be locked prior to final analyses of immunogenicity assays. Details regarding these analyses may be included as amendments to this SAP.

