8.2. Secondary

Immunogenicity will be assessed by measuring serum antibody responses by MN and/or HAI assay and mucosal antibody titers by ELISA. Additional immune parameters may be assessed including T cell responses. Samples are collected pre dose, at Day 29, and Days 1 and 29 QIV. Sample collection dates/times will be recorded in the clinical database.

Immunogenicity analyses will be analyzed as randomized. Additional details for specific immunogenicity assays may be added to this SAP as immunogenicity analyses are finalized.

Serum antibody response (influenza-specific HAI, MN, NAI, and ELISA results) will be summarized by treatment comparisons of GMT, GMFR, seroconversion, and seroprotection.

GMTs and GMFRs are displayed below by visit. Note that for approximately 40% of subjects, beginning at the end of September 2021, IP Day 29 and QIV Day 1 sample collection was on the same day.

Geometric Mean Titers and Mean Folds by Visit

Sample Collection	GMT	GMFR – reference
IP Day 1	X	
IP Day 29	X	IP Day 1
QIV Day 1	X	IP Day 1
QIV Day 29	X	QIV Day 1 & IP Day 1

Ln-transformed GMT and the ln-transformed GMFR ratios will be analyzed using t-tests. In case of baseline imbalance between treatments, analyses may be repeated using a general linear model adjusting for baseline titers.

Conversion rates categorized as >=2-fold and >= 4-fold will be reported for IP Day 29 and QIV Day 29. Treatment comparisons of conversion counts (%) will be done using Fishers Exact Tests. In case of baseline imbalance between treatments, analyses may be repeated using a logistic regression adjusting for baseline titers.

Seroprotection defined as HAI titer >=40 will be reported for IP Day 29 and QIV Day 29. Treatment comparisons of seroprotection counts (%) will be done using Fishers Exact Tests. In case of baseline imbalance between treatments, analyses may be repeated using a logistic regression adjusting for baseline titers.

Summary statistics for IgA response to influenza HA antigens are presented uncorrected and corrected for total IgA.

For the uncorrected analysis all samples are included regardless of total IgA(ug/mL).

For IgA corrected analysis

- \circ If Total IgA >= 1 then corrected value = Uncorrected/Total IgA.
- o If Total IgA < 1 then set the corrected value to missing.

For example: SingC = Sing / Total IgA >= 1; Else SingC = missing.

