10. HYPOTHESES TO BE TESTED

No formal hypotheses are to be tested. P-values for immunogenicity are descriptive only.

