11. DETERMINATION OF SAMPLE SIZE

The sample size of 80 subjects per active IP group and 40 for placebo was chosen based on reports of studies of othervaccines in early-stage development. This study is not powered for a formal comparison of IP to placebo.

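### SAP 8.2 compares the arms on serum antibody unconditionally by t-test and Fisher p-values alone, and names no between-arm estimate with a 95% confidence interval, in a study that disclaims hypotheses and power.

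*SAP*

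**What the plan says.** SAP 8.2 summarises serum antibody (HAI, MN, NAI, ELISA) by arm as GMT and GMFR at each visit, and as rates of at least 2-fold rise, at least 4-fold rise and HAI of 40 or more at IP Day 29 and QIV Day 29. SAP 1.1.1 item 5 has summaries shown by treatment and age group and for all ages combined.

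The between-arm methods in SAP 8.2 are:
- GMT and GMFR: "Ln-transformed GMT and the ln-transformed GMFR ratios will be analyzed using t-tests".
- Conversion: "Treatment comparisons of conversion counts (%) will be done using Fishers Exact Tests". Seroprotection gets the same test.
- If baseline titres are imbalanced, a baseline-adjusted linear or logistic model may follow. No imbalance criterion and no model output is named.

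Mucosal IgA gets descriptive GMTs, GMFRs and N(%), with no between-arm test.

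On the status of the tests, SAP 1.1.1 item 7 says: "There is no plan for test of hypotheses; p-values generated for immunogenicity are descriptive only and not adjusted for multiplicity". SAP 8.6 says the same in other words, and SAP 10 repeats: "No formal hypotheses are to be tested. P-values for immunogenicity are descriptive only". On power, SAP 11 says: "This study is not powered for a formal comparison of IP to placebo", and protocol 8.2.1 says: "This study is not powered for any formal comparisons".

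Neither the SAP nor protocol section 8 specifies a confidence interval, a GMT ratio or a rate difference. SAP 12 records that within-group p-values were added to the displays, and mentions no intervals.

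**The concern.** A p-value is the output of a test. Here the plan disclaims testing, yet for serum antibody the test is the one comparative method it commits to. Read on its own, a p-value cannot separate no effect from too few subjects, and it does not say how large a clear effect is.

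The groups differ greatly in size: 80 v 40 overall, 70 v 35 at age 65-85, and 10 v 5 at age 50-64. The same difference will give very different p-values across the columns of one table, and a reader may take that for a difference in response between age groups. Protocol 1.4 says that broadly reactive responses in older adults would support further development. It sets no decision rule, but a judgement of that kind rests on size and precision.

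**Working it through.** **Inputs from the documents.** "The sample size of 120 (80 active subjects and 40 placebo subjects) was chosen empirically" (SAP 1.1.1 item 6). The split is 2:1 (protocol 3.3), and the cohorts in protocol Table 1 add up: 10 + 10 + 60 = 80 active and 5 + 5 + 30 = 40 placebo. At least 4-fold seroconversion in adults aged 18-49 was 71% at 10^9 TCID50 and 28% at 10^8 (protocol 1.4).

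**Assumptions.** The documents give no placebo conversion rate and no titre SD. The response counts below, the 5% placebo rate used for power and the ln-titre SDs are illustrations. Group sizes are as planned, so evaluable sets may be smaller.

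**The plan's own figure.** The one design probability stated is more than 95% for seeing an AE of 20% prevalence in 15 subjects: 1 - 0.8^15 = 0.965. It reproduces, but it concerns safety. No precision is stated for immunogenicity.

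**Rate differences.** Let d = p1 - p2, with Wilson 95% limits (l, u) for each arm. The Newcombe interval runs from d - sqrt[(p1 - l1)^2 + (u2 - p2)^2] to d + sqrt[(u1 - p1)^2 + (p2 - l2)^2]. The p-value is two-sided Fisher.

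Worked case, 5/10 v 0/5: the Wilson limits are 0.237 to 0.763 and 0 to 0.434. The lower limit is 0.50 - sqrt(0.263^2 + 0.434^2) = -0.008. The upper limit is 0.50 + 0.263 = 0.763.

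| Active v placebo | Difference (points) | 95% CI | Fisher p |
|---|---|---|---|
| 5/10 v 0/5 | 50 | -1 to 76 | 0.10 |
| 20/80 v 4/40 | 15 | -0.4 to 27 | 0.057 |
| 16/80 v 2/40 | 15 | 1.4 to 26 | 0.032 |
| 22/80 v 1/40 | 25 | 11.5 to 36 | 0.0005 |
| 57/80 v 1/40 | 69 | 54 to 78 | <0.0001 |

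The second and third rows share a 15-point difference and have similar intervals, yet they fall on opposite sides of 0.05. In the first row the p-value hides an estimate of 50 points.

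**GMT ratio.** The 95% CI is the ratio divided and multiplied by exp[t(0.975, n1 + n2 - 2) x SD x sqrt(1/n1 + 1/n2)].
- 80 v 40, SD 1.0: exp(1.980 x 1.0 x 0.1936) = 1.47. For SD 0.8 to 1.5 the factor is 1.36 to 1.78.
- 10 v 5, SD 1.0: exp(2.160 x 1.0 x 0.5477) = 3.3. For SD 0.8 to 1.5 it is 2.6 to 5.9.

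The SD enters directly, so two per-arm GMTs do not determine the interval.

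**Fisher power at 5% placebo conversion** (exact enumeration, two-sided 0.05; the SAP states no alpha):

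| Active rate | 10 v 5 | 80 v 40 |
|---|---|---|
| 28% | 3% | 90% |
| 50% | 29% | >99.9% |
| 71% | 70% | >99.9% |

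Weak power is a feature of the 10 v 5 group and does not carry over to the overall comparison.

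**The case against.** **A reader might infer that the effect size is never reported.** The documents do not support this. Means and rates are shown by arm, age group and overall, so point ratios and differences follow directly. An interval for a rate difference can be rebuilt from N(%). For GMT and GMFR, an SE could be backed out of the ratio and an exactly printed t-test p-value, but not from one that is heavily rounded or shown only as below a threshold. That is a repair by the reader and not a planned output.

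**A reader might extend the point to all immunogenicity.** It does not reach mucosal IgA, a secondary endpoint for which no between-arm test is planned.

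**A reader might conclude that the trial is too small for immunogenicity.** The 80 v 40 power column does not bear that out under the stated assumptions. Protocol 1.4 has the 50-64 group enrolled first to assess safety, so its low power is no defect of SAP 8.2.

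**Regression models are also named.** They would give estimates, but they are optional and their outputs are unstated.

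**The table shells are not in the text reviewed, and SAP 1.1.1 item 9 and SAP 8.2 allow later detail.** The shells may contain intervals, so this point concerns what the SAP text specifies. An addition that may be made is not yet pre-specified.

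**The planned outputs match the endpoints.** Protocol 2.2.2 defines numbers and percentages of responders, and protocol 8.4 promises descriptive statistics. Both are delivered by arm, so the plan breaks no promise. That limits the severity. It does not explain why, once a comparison is made, its only committed form is a p-value.

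**Conclusion.** The point holds for serum antibody in this form: results are reported by arm, the unconditional arm comparison is by p-value, and no between-arm estimate with its uncertainty is specified. The gap matters most for the GMT and GMFR ratios, whose intervals need a spread or SE that SAP 8.2 does not name as an output. With an assumed ln-SD of 0.8 to 1.5, the unreported uncertainty is a factor of 1.36 to 1.78 overall and 2.6 to 5.9 at age 50-64.

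Severity is modest. Nothing is biased, no primary endpoint or safety analysis is touched, and the p-values are plainly labelled descriptive. The examples rest on assumed response counts, placebo rates and SDs, and the 71% and 28% rates come from a younger population. The finding about what the SAP specifies does not depend on them.

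**What to change.** In SAP 8.2, for each serum assay and visit, overall and by age group, specify:
- the M2SR/placebo ratio of GMTs, and of GMFRs for each reference visit listed, with 95% CIs back-transformed from the ln-scale analysis;
- the M2SR minus placebo difference in rates of at least 2-fold and at least 4-fold conversion and of HAI of 40 or more, with Newcombe or Miettinen-Nurminen 95% CIs (one method named in advance).

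The existing p-values may stay as secondary, descriptive columns; removing them is a matter of taste. The cost is a few sentences of SAP text and extra columns in the table shells, from the same data and software. SAP 1.1.1 item 9 already foresees amendments for the immunogenicity analyses, so the change fits there.

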SAEs occurring at any time during the study will be recorded. Administration site and solicited AEs will be recorded through 7 days after IP vaccination (Day 8). Unsolicited AEs will be recorded from time of consent through 28 days after both M2SR and QIV vaccinations.

While safety and tolerability are the primary objectives, this clinical study is also designed to assess the immune response to one dose of the investigational vaccine and after subsequent immunization with QIV. Immunogenicity will be assessed by measuring serum antibody responses by MN and/or HAI assay and mucosal antibody titers by ELISA. Additional immune parameters will be assessed including T-cell responses. Subjects will be screened to determine HA titers against the target component (A/Singapore/INFIMH-16-0019/2016 [H3N2]) with the intent to enroll subjects with low titers (≤320 HAI titer).

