1.1.2.3. Treatment Blinding

ClinDart Data Management (DM) is responsible for supporting ongoing blinded data review and tracking throughout the study. DM will have access to treatment codes only after the database is locked. North Rim Consulting Statistician and programming staff will have access to treatment codes throughout the trial and will be responsible for managing information so as not to unblind other team members.

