Summaries are GMTs, GMFRs, and N(%) of subjects with >= 2-fold and > = 4-fold rise in mucosal IgA. Summary statistics for secretory IgA immune response (influenza A-specific and total IgA ELISA) at IP Day 1, IP Day 29, and QIV Day 29 will be provided.

Depending upon the results of primary and secondary analyses, some or all the following exploratory analyses may not be done. Cell-mediated immunity (CMI) assessed by frequencies and fold-increases of antigen-specific T-lymphocytes may be summarized. Additional influenza-specific assays may be performed, and results summarized. Results of exploratory analyses may be reported separately from the CSR.

T Cell Mediated Immunity (Cytokines: IFNg, GrzB, IFNg+GrzB)

T Cell-mediated immunity (CMI) results are available for cells that secrete IFNg only, GrzB only, and cells that secrete both IFNg and GrzB. These double-secreting cells (IFNg+GrzB) will be a subset of cells that secret IFNg or GrzB only. CMI results are reported in Spot Forming Colonies (SFC) per 400,000 cells.

Summaries are GMTs, GMFRs, and N(%) of subjects with \geq = 2-fold and \geq = 4-fold rise in CMI. Summary statistics for CMI at IP Day 1 and IP Day 29 will be provided.

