12. CHANGES IN THE CONDUCT OF THE STUDY OR PLANNEDANALYSES

Unavailability of some pre-dose Day 1 samples made it necessary to replace these samples with Screening samples.

Screening results used to stratify treatment assignment were replaced in data presentations by HAI results generated at Flugen.

Descriptive p-values for within-group changes (GMFR) were added to displays.

Antigen specific T cell values were completed at Flugen and levels reported to NRC for analyses. Documentation of the pre-processing of samples are documented at Flugen.

E-diary data collection and transfer initially proved problematic. Issues were resolved and data transfers corrected by the vendor. Corrected e-diary data will be presented in the CSR. Original values will be listed in an appendix.

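### SAP 8.2 allows completed T-cell analyses to be left out depending on the primary and secondary results, with no criterion, and contradicts itself on whether they will be reported

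*SAP*

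**What the plan says.** The relevant SAP text is in section 8.2.

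- **The condition:** "Depending upon the results of primary and secondary analyses, some or all the following exploratory analyses may not be done". The trigger is the results. No direction, threshold or decision-maker is given.
- **The first analysis it covers:** "Cell-mediated immunity (CMI) assessed by frequencies and fold-increases of antigen-specific T-lymphocytes may be summarized". Additional influenza-specific assays follow.
- **Where output may go:** "Results of exploratory analyses may be reported separately from the CSR".
- **State of the data:** "T Cell-mediated immunity (CMI) results are available for cells that secrete IFNg only, GrzB only", and also for double-secreting cells. SAP 12 adds: "Antigen specific T cell values were completed at Flugen and levels reported to NRC for analyses".
- **A commitment in the other direction**, closing the CMI text of the same section: "Summary statistics for CMI at IP Day 1 and IP Day 29 will be provided". The sentence before it fixes the displays as GMTs, GMFRs and the number and percentage with 2-fold and 4-fold rises.

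Protocol 2.1.3 and 2.2.3 list cellular responses as an exploratory objective and endpoint, without any condition on other results. Protocol 3.1 says "Additional immune parameters will be assessed including T-cell responses"; the protocol synopsis and the opening of SAP 8.2 say only that they may be. Protocol Table 2 schedules 50 mL for PBMCs at V01 and V03. SAP 1 gives the SAP precedence where the two documents disagree.

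**The concern.** A plan may reasonably leave optional assays unrun. It is different to let the serology and safety results decide whether data already in hand are tabulated. If CMI is shown only when serology looks good, it may seem to be independent support when it is not. If it is shown only when serology disappoints, a reader may take it for the planned analysis when it was a fallback. Nothing in the SAP would let a CSR reader tell these cases apart from unconditional reporting. Calling the endpoint exploratory, and its p-values descriptive, deals with multiplicity but not with omission.

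The setting makes such selection feasible. SAP 1.1.1 places database lock before the final immunogenicity analyses and lets their details be added by amendment. SAP 1.1.2.3 states that "North Rim Consulting Statistician and programming staff will have access to treatment codes throughout the trial". If NRC in SAP 12 is that group, which is an inference, the T-cell values and the treatment codes are in the same hands before the decision is made.

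At stake is how far the CMI results can be trusted when the next studies are planned. Protocol 1.4 puts weight on cellular immunity as something inactivated vaccines do not elicit.

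**Working it through.** **Step 1: the SAP statements on CMI side by side**

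| Place | Status of CMI |
|---|---|
| SAP 8.2, conditional sentence | may not be done, depending on results |
| SAP 8.2, next sentence | may be summarised |
| SAP 8.2, CMI text, opening | results available |
| SAP 8.2, CMI text, end | summaries at IP Day 1 and IP Day 29 will be provided |
| SAP 12 | values completed and passed on for analysis |

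The last sentence of SAP 8.2 does not withdraw the condition, and the condition does not exempt CMI. Both readings are open. Because the values exist, the condition saves no assay cost for CMI.

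**Step 2: scope.** The condition reaches CMI and the additional assays. The serum and mucosal responses after QIV, which Protocol 2.1.3 also calls exploratory, are reported in SAP 8.2 without condition.

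**Step 3: illustration of size.** The documents give no gate, no correlation and no design figure for CMI, so there is no figure of the plan's own to reproduce. Assumptions:

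- Z1 (serology) and Z2 (CMI) are bivariate normal with unit variance and correlation r.
- There is no true CMI effect, so Z2 has mean 0.
- CMI is displayed only if Z1 > 1.96, which is favourable at two-sided p<0.05.
- The mean of Z1 is set so that the chance of passing, P, is 2.5% (no serology effect), 50%, 80% or 99%.

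The quantity is P(Z2 > 1.96 given Z1 > 1.96) = P(both > 1.96) / P. Without selection it is 2.5%.

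| P | r = 0 | r = 0.2 | r = 0.5 | r = 0.8 |
|---|---|---|---|---|
| 2.5% | 2.5% | 6.4% | 18% | 44% |
| 50% | 2.5% | 3.4% | 4.5% | 5.0% |
| 80% | 2.5% | 2.8% | 3.1% | 3.1% |
| 99% | 2.5% | 2.5% | 2.5% | 2.5% |

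For example, at P = 2.5% and r = 0.5 the joint probability is 0.00462, and 0.00462 / 0.025 = 0.185.

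**Step 4: the same on the estimate scale.** SAP 8.2 specifies no between-group test for CMI, so bias in the displayed estimate is also useful. It equals r × φ(c) / P in standard errors, where φ is the normal density and c is the normal quantile at 1 − P. At P = 2.5%, φ(1.96) / 0.025 = 2.34, giving 0.70 SE at r = 0.3 and 1.40 SE at r = 0.6. At P = 50% the values are 0.24 and 0.48 SE; at 80%, 0.10 and 0.21 SE; at 99%, at most 0.02 SE.

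**Step 5: the opposite gate.** If CMI is displayed only when serology is not favourable, the quantity is (0.025 − joint) / (1 − P). At P = 2.5% and r = 0.5 this is (0.025 − 0.00462) / 0.975 = 2.1%. With positive correlation, then, the fallback use does not raise the chance of a favourable CMI result. The harm there is that the reader does not know the display was conditional.

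**The case against.** The best reply is that SAP 8.2 itself promises CMI summaries at IP Day 1 and IP Day 29, names three readouts and fixes the displays. On that reading the sponsor means to report CMI and the conditional sentence is loose drafting. This stands in part. It shows probable intent, and it rules out inferring that CMI results are in fact being selected; the wording grants a permission and no more. It does not remove the permission, because nothing says which sentence governs.

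Other points stand as limits.

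- The protocol is not uniform: section 3.1 commits to T-cell assessment, while the synopsis leaves it optional. A reader of 3.1 alone might infer a firm commitment that the SAP breaks, and the documents do not support that. They do show that no protocol text ties CMI to other results.
- The larger figures need a vaccine with no serological effect. Protocol 1.4 reports 71% seroconversion at this dose in adults aged 18-49, which points to the lower rows of the table. Protocol 1.2.1 notes weaker influenza vaccine responses in older adults, so the upper rows are not excluded.
- A correlation between serology and CMI is assumed; the documents give none.
- For assays not yet run, a condition can save sample and money, and Protocol 2.2.3 already makes them optional. Reporting outside the CSR is declared openly. How strictly to treat these two is partly preference.

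**Conclusion.** The point holds as a selective-reporting risk of modest weight. SAP 8.2 permits analysis of completed CMI data to be omitted on the strength of other results, without a criterion, and also says the summaries will be given. These statements must be reconciled.

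Under an assumed serology gate at p<0.05 and no true CMI effect, the chance of a favourable displayed CMI result runs from 2.5% (strong serology effect, or no correlation) to 18% (no serology effect, correlation 0.5) and 44% (no serology effect, correlation 0.8). This is a range and not a forecast.

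A reader might infer that the trial's error control or main conclusions are damaged. The documents do not support that: safety is primary, SAP 8.6 and 10 make all p-values descriptive with no hypotheses tested, and no primary or secondary conclusion depends on CMI.

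**What to change.** In SAP 8.2, remove CMI from the conditional sentence and replace the permissive wording on its summary with a commitment along these lines: all three completed CMI readouts (IFNg, GrzB, IFNg+GrzB) will be summarised by treatment at IP Day 1 and IP Day 29, regardless of the primary and secondary results, in the CSR or a named addendum to it. That agrees with the sentence that already closes the section.

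For optional assays not yet run, keep the discretion but list in the CSR any that were not done, with the reason.

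The cost is a short SAP edit and a few tables from values already passed on for analysis. The downside is that the report carries exploratory tables that might otherwise have been left out.
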